**13.9 24 HOURS (RANGE 16-36HRS) POST-PROCEDURE**

Subjects will undergo standard of care assessment post EVT procedure according to the current practice of the hospital.

The following data will be collected:

- CT/CTA / MRI/MRA if available per local hospital practice (range 2hrs - 36hs post procedure)
- Concomitant medications, including Anti-thrombotic treatments
- Adverse events and Serious Adverse events

For all subjects that decease prior to the 24H (range 16-36hrs) assessment, available information regarding the primary cause of death and date/time of death will be recorded.

**13.10 MANAGEMENT OF PATIENTS AT THE END OF THE STUDY**

Patient management beyond the participation in this study should be according to the standard of care of the investigational site and/or treating physician.

**Clinical investigation plan - CLOT OUT****14 STUDY HANDLING PROCEDURES****14.1 HISTOPATHOLOGICAL CLINICAL PROTOCOL**

The following instructions will be provided to the site, for shipment of the Retrieved clots to the Core Laboratory:

- In the procedure room, set the clot into Formol solution (Formaldehyde 4% = 10% formalin solution). As an example, reference VWR FOR0020AF59001 can be used but any other solution of similar composition will be acceptable.
- Identify the clot with the subject study number.
- Send the clot to the pathology lab for paraffin embedding. Clots needs to be in the formol solution for at least 24h before paraffin embedding.
- Send paraffin embedded clots to the Core Histology Laboratory.

An operation manual will provide detailed information on the handling and processing of the clots.

**14.2 RETURN OF USED CLOTILD® SMART GUIDEWIRE TO SPONSOR**

- Used Clotild® Smart Guidewires will be washed with sterile saline, rolled up and stored in a biohazard plastic bag (provided by the sponsor) with device number indicated.
- Up to 5 devices will be stored before shipment to SENSOME for physical inspection.

An operation manual will provide detailed information on the handling and processing of the used devices which will also be summarized in section 8.

**15 STATISTICAL CONSIDERATION****15.1 STATISTICAL ANALYSES**

Sponsor may assign a third party to be responsible for statistical analyses.

A general description of the planned statistical methods to be used to analyze the data collected in this study is presented in the following subsections.

Additional details will be provided in the Statistical Analysis Plan.

Given the fact that this is a single arm clinical trial no statistical comparisons will be performed. For the primary safety endpoint, statistical analysis will consist only of descriptive analysis. For performance endpoints, statistical analyses will consist of descriptive analysis of prediction performance estimators and correlation analyses with statistical modelling.

**Clinical investigation plan - CLOT OUT****15.2 ANALYSES POPULATION**

This study will be conducted in subjects presenting an acute ischemic stroke due to M1 occlusion, eligible for EVT based on neuro-interventionist and/or neurologist investigators' opinion.

Intention To Treat (ITT) Population

All patients who were enrolled, so all patients (or legally authorized representatives) who signed and dated the patient information consent form even though the CSGS was not used in the subject.

The **safety analysis** (amount of AE) will be performed on the intention to treat (ITT) population.

Treated Population

All patients in which the guidewire went through the sheath, even though if not all eligibility criteria were met or if a device failure occurred or if the clot could not be retrieved.

The **primary safety endpoint** will be determined on the Treated Population.

Per-protocol Population

All patients from the Treated Population who comply to all eligibility criteria.

No separate analyses will be performed for the per-protocol population.

Development Performance Population

This population includes patients from whom at least 1 evaluable acquisition was captured by the CSGS. An evaluable acquisition is defined as a "CLOT tag" or "Clot or beyond" tag with non-anomalous (see criteria section 15.6) impedance measurement. Data of this population will be used during the development phase to build the different models for classification of RBC-positive and platelet-positive.

Local-Scale Performance Population

This population includes patients for whom non-anomalous acquisition was collected by the CSGS during at least one tagged measurement with clot contact excluding patients from the Development Performance Population. Data of this population will be used during the validation phase to validate the model built during the development phase.

The analysis of the **primary performance endpoint** will be performed on data from the Local-Scale Performance Population.

Clot-Scale Performance Population

All patients from the Local-Scale Performance Population of which the clot could be retrieved for histological assessment.

Performance evaluation of the secondary performance endpoints related to the clot scale will be done on the Clot-Scale Performance Population.

**Clinical investigation plan - CLOT OUT****15.3 DEVELOPMENT PHASE AND VALIDATION PHASE OF CSGS PREDICTION MODEL**

A major objective of this study is to evaluate the prediction model(s) of the Clotild® Smart Guidewire System. These prediction models are based on physical properties of the impedance measurements captured by the sensor, complemented with a comparison to suitable labels for each endpoint (a.k.a. phenomenological modelling). The impedance dataset that will be constructed during the clinical investigation should serve to develop the prediction models (model development) and to evaluate their prediction accuracy (model evaluation). Such an evaluation methodology is inspired from *Good Machine Learning Practice for Medical Device* and avoids any optimistic bias.

To this end, the study is split in two phases:

- **the development phase**, where model optimization is being made to arrive at a single prediction model per endpoint developed on the full development dataset.
- **the validation phase**, that is solely used to assess the generalization performance of the model(s) developed during the development phase.

In order to develop the prediction model(s), data from the development dataset are analysed on an ongoing basis.

When moving to the validation phase the model(s) shall be locked, remaining unchanged during the course of the validation phase.

This procedure of splitting the dataset into two independent datasets will be performed for the primary performance endpoint assessment as well as for the secondary and tertiary endpoint assessments where prediction is done.

**15.4 ENDPOINT ANALYSIS****15.4.1 Primary Endpoint analysis**

For the **Primary Safety Endpoint** descriptive statistics will be provided showing the proportion of patients with intracranial vessel perforation and / or dissection due to Clotild® usage. Furthermore, a 95% confidence interval will be estimated. The primary safety endpoint will be determined in all patients in whom the guidewire went through the introduction sheath.

The **Primary Performance Endpoint** is defined as the ability to perform binary classification of individual electrophysiological parameter measurements (local scale) by distinguishing local regions with substantial red blood cell content (RBC-positive) from regions with negligible red blood cell

---

 *Good Machine Learning Practice for Medical Device Development: Guiding Principles (FDA, October 2021)*

**Clinical investigation plan - CLOT OUT**

content (RBC-negative) in the occlusion. This endpoint can be understood as the ability for an automated system to rank individual electrophysiological measurements in the occlusion according to the local scale content of RBC (the predicted RBC-content score). Evaluation is based on expert labelling of individual electrophysiological measurements as a binary outcome: RBC-positive (region with substantial RBC content) and RBC-negative (region with negligible RBC content). This labelling, considered as ground truth, is made by (at least) two independent SENSOME experts that cumulate the relevant experience in electrochemical impedance measurements of different biological tissues from previous non-clinical research.

- The performance of the CSGS model will be assessed by the performance metric Area Under the Receiver Operator Characteristic curve (AUC of ROC) computed from the RBC-content score predicted on the validation dataset only.
- The ROC curve will be defined by the sensitivity (true positive rate) on the Y-axis and 1-specificity (false positive rate) on the X-axis. The ground truth is defined as the binary classification of the local regions into RBC-positive or RBC-negative content performed by SENSOME experts.
- The comparator will be the binary classification score determined by the CSGS model. The CSGS model will be developed using interventions from the development phase (Development Performance Population) while it will be validated on the impedance data from the validation phase (Local-Scale Performance Population).

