**Validation set size**

The minimum number of  **$N_V$  interventions** to be included in the validation dataset to estimate the performance  $\hat{A}$  with sufficient statistical confidence margin is determined, with  $\hat{A}$  the area under the ROC curve (AUC) of the prediction model obtained on the validation sample of the population.

The following assumptions are made:

- **Estimated average number of independent individual measurements from a single tagged acquisition with clot contact = 5.44** (based on the quality check of data collected in the first 9 procedural successes)
- **Estimated average number of tagged acquisitions with clot contact per intervention = 3** (based on the quality check of data collected in the first 9 procedural successes)
- **Estimated number of RBC-positive cases = 53%** (based on the quality check of data collected in the first 9 procedural successes)
- **Expected number of RBC-negative cases = 47%**
- **An AUC of 0.85 is assumed with a maximal width of 0.1 for the 95% confidence interval**

With these assumptions, using the Hanley and McNeil estimate (Hanley and McNeil 1982) for the confidence interval to reach an expected AUC of 0.85 and a maximal width of the 95% confidence interval of 0.1, a number of  **$N_V = 14$  interventions** with at least 1 evaluable measurement valid interventions are necessary for the validation set (Local-Scale Performance Population).

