## 2. Study objective

The objective of the study is to evaluate the safety and the possibility of Clotild® Smart Guidewire System (CSGS) to provide electrophysiological measurements. The electrophysiological measurements will be used to update CSGS's database and thus improve the prediction accuracy of the model in providing physicians with insights for mechanical thrombectomy.

The **primary objective** of the study is to evaluate the **safety** of using Clotild® Smart Guidewire System (CSGS) at the occlusion location during an EndoVascular Thrombectomy (EVT) procedure for the treatment of subjects with acute ischemic stroke eligible for EVT.

Safety will be evaluated by means of the amount of intracranial vessel perforations and/or dissections with the CSGS during the procedure.

The **secondary objective** of the study is to evaluate the **performance** of CSGS, defined here as the feasibility to measure electrophysiological properties of the occlusion in vivo during EVT procedures for the treatment of acute ischemic stroke.

Performance will be evaluated by the ability to correctly binary classify the clot as Red Blood Cell (RBC) positive or RBC negative, platelet positive or negative and fibrin positive or negative. Performance endpoints that focus on clot characterization are split in two categories: one category that demonstrates the ability of an automatic system to correctly identify the local composition of a clot

(local-scale), and the other category that reveals the extent of concordance between a number of local scale measurements made from the CSGS and the histological characterization by the Core Laboratory (Core Lab) of the full clot retrieved during the EVT procedure (clot scale).

The **tertiary objective** of the study is to explore possible relationships between CSGS measurements and intervention parameters such as first pass effect, number of passes to successfully retrieve the clot and other key parameters. Due to the nature of the tertiary objectives, not all centers may contribute to the data collection.

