### b) Primary Performance Endpoint

The Primary Performance Endpoint is defined as the ability to perform binary classification of individual electrophysiological parameter measurements by distinguishing local regions with substantial red blood cell content (RBC-positive) from regions with negligible red blood cell content (RBC-negative) in the occlusion. This endpoint can be understood as the ability for an automated system to rank individual electrophysiological measurements in the occlusion according to the local scale content of RBC (the predicted RBC-content score).

The ability to perform binary classification will be evaluated by the sensitivity (true positive rate) and the specificity (false positive rate) for varying detection threshold. Based on those 2 metrics, the Area under the Receiver Operator Characteristic curve (AUC of ROC) and its 95% confidence intervals (CI)

will be calculated. An AUC of 0.85 is assumed computed from the RBC-content score predicted on the validation dataset only with a maximal width of 0.1 for the 95% confidence interval.

The 'gold standard' is defined as the binary classification of the local regions into RBC-positive or RBC-negative content performed by the Sensome experts. This labelling, considered as ground truth, is made by (at least) two independent SENSOME experts that cumulate the relevant experience in electrochemical impedance measurements of different biological tissues from previous non-clinical research. The comparator will be the binary classification determined by the CSGS model developed by phenomenological modelling. The model will be developed on the data of the development dataset while it will be validated on the data of the validation dataset.

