The single electrode pair measurement is defined as the response to an applied micro-current through an electrode pair. Such a response is referred to as 'the electrophysiological parameter': it depends on the arrangement and type of cells and interspersed biochemical components. The response across a single electrode pair is composed of a set of real numbers (up to 32 for CSGS) which are not independent; this set of numbers is referred to as a 'spectrum' since it forms the response as the micro-current frequency is swept across a pre-defined range. This is also referred to as a 'local-scale measurement'. A measurement triggered by the Cloviz software collects at a given time point the spectrums from a pre-defined set of electrode pairs. This is also referred to as a 'sensor-scale measurement' since it sweeps the electrode pairs of the sensor.

The CSGS will be inserted and up to 6 measurements will be done: 1 measurement distal to the access catheter in circulating blood (this is the reference measurement), 1 measurement proximal to the site of occlusion, 2 to 3 measurements inside the occlusion and 1 measurement at the most distal advancement of the guidewire (ideally distal to the occlusion). The collection of measurements made in contact with the clot is referred to as the 'clot-scale' measurement.

[figure not shown]

Figure 1: Schematic view of the sensor presenting the different scales of measurements.

Data from the CSGS is synced to the cloud database. These data are processed offline. Individual electrophysiological measurements are annotated manually by Sensome experts by inspecting the signal and the histological content from the full clot.

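### The primary performance AUC mixes between-clot with within-clot discrimination, so by itself it cannot show that the device tells regions apart inside one occlusion

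*Protocol*

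**What the plan says.** Protocol section 15.4.1 explains the primary performance endpoint as "the ability for an automated system to rank individual electrophysiological measurements in the occlusion according to the local scale content of RBC". The metric is an AUC "computed from the RBC-content score predicted on the validation dataset only". SAP section 4.b adds that performance "will be evaluated by the sensitivity (true positive rate) and the specificity (false positive rate) for varying detection threshold", from which the AUC and its 95% interval follow.

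SAP section 2 divides the clot-characterisation endpoints into two categories. The local-scale one is "one category that demonstrates the ability of an automatic system to correctly identify the local composition of a clot"; the other is agreement with the histology of the whole retrieved clot. Secondary endpoints 4 (platelets) and 6 (fibrin) reuse the primary endpoint's methodology.

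On sizing, protocol section 15.5 and SAP section 6 state: "An AUC of 0.85 is assumed with a maximal width of 0.1 for the 95% confidence interval". They also give "Estimated average number of independent individual measurements from a single tagged acquisition with clot contact = 5.44" and "Estimated average number of tagged acquisitions with clot contact per intervention = 3", with a 53/47 split of RBC-positive and RBC-negative readings and 14 validation interventions. SAP section 8.c.i says that intervals come from the bootstrap but names no resampling unit. Neither document mentions a stratified, clustered or within-intervention AUC.

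**The concern.** An AUC is the share of positive/negative pairs that the score puts in the right order. When readings from many patients enter one ROC curve, most pairs set a reading from one clot against a reading from another. Such a pair can be ordered correctly because the score sees the local tissue, or merely because it separates RBC-rich patients from RBC-poor ones. The pooled AUC does not tell these apart.

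At stake is what the trial can say about local sensing. The clot-scale secondary endpoints (1, 5 and 7) are themselves between-clot correlations, and secondary endpoints 4 and 6 inherit the pooled metric. No planned composition analysis therefore isolates discrimination inside one occlusion. The labelling may add to the mixing: readings are "annotated manually by Sensome experts by inspecting the signal and the histological content from the full clot", which could make labels within a clot more alike. The point does not depend on that, however. It would remain with perfect labels and with a patient-level bootstrap, because it concerns which quantity is estimated.

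**Working it through.** **1. Reproduce the plan's sizing.** Inputs from protocol section 15.5: AUC A = 0.85; 3 x 5.44 = 16.32 readings per intervention; 53% RBC-positive.

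Hanley-McNeil: Var = [A(1-A) + (n₊-1)(Q₁-A²) + (n₋-1)(Q₂-A²)] / (n₊n₋), with Q₁ = A/(2-A) = 0.7391 and Q₂ = 2A²/(1+A) = 0.7811.

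- N = 14: 228.48 readings, n₊ = 121.1, n₋ = 107.4, SE = 0.02535, width = 2 x 1.96 x SE = 0.0994.
- N = 13: 212.16 readings, width = 0.103.

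So 14 is the smallest number that meets a width of 0.1, and it does so with all readings in a single pool. This is the evidence for pooling.

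**2. Share of cross-clot pairs.** If every clot had the same 53/47 mix:

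- all pairs: 121.09 x 107.39 = 13,004;
- within-clot pairs: 14 x (16.32 x 0.53) x (16.32 x 0.47) = 929, or 1/14 = 7.1%;
- cross-clot pairs: 92.9%.

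If clots differ in RBC share, fewer pairs lie within a clot and the cross-clot share rises.

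**3. A score with no within-clot information.** The documents do not give the between-clot SD of the RBC-positive share, so a range is assumed. Simulation: 14 clots, 16 readings each; clot share drawn from a Beta distribution with mean 0.53; labels Bernoulli given the share; score equal to the clot's share, with or without a clot-level error of SD 0.2, plus negligible noise to break ties. ICC = SD²/(0.53 x 0.47).

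| SD of share | ICC | Cross-clot pairs | Mean pooled AUC, perfect clot ordering | Mean pooled AUC, clot error SD 0.2 | Within-clot AUC |
|---|---|---|---|---|---|
| 0.15 | 0.09 | 94% | 0.66 | 0.60 | 0.50 |
| 0.20 | 0.16 | 94% | 0.72 | 0.65 | 0.50 |
| 0.25 | 0.25 | 95% | 0.77 | 0.72 | 0.50 |
| 0.30 | 0.36 | 96% | 0.83 | 0.78 | 0.50 |
| 0.35 | 0.49 | 96% | 0.89 | 0.84 | 0.50 |

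Closed-form check: if the share is uniform on 0 to 1 and the score equals it, the pooled AUC is 5/6 = 0.833, in line with the table (a uniform share has SD 0.29).

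**4. The opposite error.** Take a binormal score with within-clot AUC 0.85, so the separation is √2 x Φ⁻¹(0.85) = 1.466 reading-SDs. Add a patient offset with an SD of one reading-SD. A cross-clot pair is then ordered correctly with probability Φ(1.466/√(2 + 2 x 1²)) = Φ(0.733) = 0.768. Weighting by pairs: 0.929 x 0.768 + 0.071 x 0.85 = 0.77. With an offset of 1.5 reading-SDs the same steps give 0.73.

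**5. Precision of a within-intervention AUC.** With equal mixes, each clot has 8.65 positive and 7.67 negative readings, so the Hanley-McNeil SE per clot is 0.0986. Averaged over 14 clots, the width is 3.92 x 0.0986/√14 = 0.103. With unequal mixes the simulated width was about 0.11 to 0.16. The share of interventions with only one label class, which supply no pairs, ran from about 0% to 28% over the assumed range.

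**The case against.** The strongest reply is that a pooled AUC is the right figure for this device. Protocol section 8.1.1 defines local scale by the electrode pair, which is a unit of measurement rather than a contrast between sites in one clot. The reference to the occlusion may mean only readings with clot contact, as opposed to blood or vessel wall. The model is locked before validation, and a single threshold applied across patients is properly judged across patients. This stands, and it is why the pooled AUC should remain primary. It does not close the gap: SAP section 2 separates local from clot-scale ability, and the planned analyses cannot.

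A second reply is that the zero-information score in step 3 is artificial. SAP section 8.c.i gives the model input as the impedance spectrum of each electrode pair. If the score depends only on local tissue, its distribution given the label is the same in every clot and the two AUCs coincide. This also stands. The documents neither show nor exclude a patient-level component in the signal, so the concern is conditional on one.

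Two stronger readings are tempting. One is that, because about 95% of pairs are cross-clot, a model blind to local structure would score close to 0.85. The documents do not support that. A high cross-clot share does not alone produce a high AUC; values near 0.85 need an assumed SD of about 0.30 or more together with near-exact ordering of clots. With clot-level error of SD 0.2, 0.85 was reached in 0% to 48% of runs across the range. The other is that an interval excluding 0.5 for such a score would be a false positive. In these scenarios the pooled AUC truly exceeds 0.5, and no test against 0.5 is planned. Nor is 0.85 a pass mark; it is a planning value for precision.

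**Conclusion.** The concern holds in a limited form. As sized, the primary AUC is pooled, which is an inference from the arithmetic and from the absence of any stratified analysis. From the plan's own inputs, at least 93% of its pairs are between clots, rising to about 94% to 96% if clots differ in RBC share as assumed above. It therefore cannot by itself support a statement that the device distinguishes regions inside an occlusion.

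How far it could mislead depends on two things the documents do not give: the between-clot spread of the RBC-positive share, and whether the score carries a patient-level component. Without such a component there is no discrepancy. With one, the pooled figure may be too high (0.60 to 0.89 against a within-clot 0.50, over the assumed range) or too low (about 0.77 against 0.85). The primary analysis is not invalid; it needs a companion figure.

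**What to change.** In protocol section 15.4.1 and SAP section 4.b:

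- Keep the pooled AUC as the primary performance figure, and say in words that it pools readings across interventions.
- Pre-specify beside it a within-intervention AUC: concordance over RBC-positive/RBC-negative pairs from the same intervention, summed over interventions and weighted by pair count, with a 95% interval from a bootstrap that resamples patients.
- Report how many interventions have only one label class.
- State that any wording about distinguishing regions within an occlusion must be supported by the within-intervention figure.
- Do the same for secondary endpoints 4 and 6.

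The cost is a short text change and a few lines of code on data already collected; no further patients are needed. The drawbacks are a somewhat wider interval (about 0.10 to 0.16) and no contribution from single-class interventions. The added figure also gives no credit for correctly scoring a uniformly RBC-rich or RBC-poor clot, which is another reason to retain the pooled AUC.
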